Objectives:

Primary objective: To undertake an ethical and independent study to determine whether there is any significant difference in the efficacy of interdental brushes (Brand: “Curaprox” vs Oral Irrigation (Brand: “Waterpik” Pic Pocket TM subgingival irrigation tip) in the removal of plaque and the maintenance of periodontal health.

Secondary objectives: To investigate the patient preference and ease of use for the interdental brushes and Oral Irrigation.

Study design: Within-subjects experimental study design

Planned sample size: 40 subjects would be enrolled into the study.

Selection criteria:

1. Disease status/ or disease group for study: Embrasure space of 2 or 3. PSR code \leq 3.
2. Gender: no restrictions
3. Age range: >18 years
4. At least 24 natural teeth
5. Willingness to provide informed consent and willingness to participate and comply with the study requirements.

Study procedure

Visit 1: Participant enrolment, gain consent; initial full mouth debridement - 2-week break for “Washout”

Visit 2: Clinical parameters would be assessed by clinical examination by two calibrated, blinded examiners (qualified research assistants); dental plaque/stain and supragingival calculus removal; randomised allocation. Participants would use their allocated interproximal aid for 4 weeks.

Visit 3: Clinical parameters will be assessed, and Oral photographs taken. 2-week break for “Washout”.

Visit 4: plaque removed only. Participants would receive OHI and use their allocated interproximal aid for 4 weeks.

Visit 5: Clinical parameters will be assessed, Oral photographs taken; Final AirFlow provided. Participants to complete qualitative satisfaction survey.

Statistical considerations

Sample size calculation: 40 subjects would be enrolled into the study. A sample size calculation determined 34 participants were required for an effect size of 0.4 (medium sample size approach), with $\alpha=0.05$ and $\beta=0.85$ (G*Power sample calculation software). An additional 20% is included to allow for dropouts.

Analysis plan: The analysis will be performed using PRISM (Version 8) statistical software, with the level of significance set at $p<0.05$. The difference in clinical parameters between baseline, and between interventions, will be evaluated using a “Paired t-test”.

Duration of the Study: up to 2 years

1. BACKGROUND AND INTRODUCTION

1.1. DISEASE/PROPOSED INTERVENTION BACKGROUND

Background Information

Interdental Brushes

There is a significant amount of evidence advocating the use of Interdental Brushes as an effective interdental cleaning aid. A systematic review Slot et al. (2008) highlights the effectiveness of inter-dental brushes as an adjunct to toothbrushing for plaque removal in adult patients. This systematic review also revealed a positive statistical reduction in interdental biofilm when using inter-dental brushes as compared to floss at a control. However, this review also showed that there was no difference in gingival inflammation or bleeding. Interestingly, criteria for selecting adult patients varied throughout the studies reviewed. Health status was not identified in three studies, and health status was reported as “good general health” in six studies. Although all studies included patients, who had inter-dental spaces that could accommodate the use of an inter-dental brush, three studies did not report on the subjects’ periodontal status. The diversity in selection of study subjects was quite significant amongst these studies which may well have affected the robustness of the conclusions of the review (Gluch 2012).

However, the sample size of the different trials within this review can be considered large enough to validate statistical and clinically significant differences (Rasines 2009). In a Cochrane review, Poklepovic et al. (2013) reviewed seven studies about inter-dental brushes (total 354 participants analysed). Only one reported objective comparison of toothbrushing with and without inter-dental brush use. The review identified very low-quality evidence that inter-dental brushing in combination with toothbrushing is more beneficial than toothbrushing alone for gingivitis and plaque at the 1-month time frame. Further, there was also low-quality evidence from seven other studies identifying that inter-dental brushing reduces gingivitis when compared with flossing, but these results were only found at 1 month. There was insufficient evidence to determine whether interdental brushing reduced levels of biofilm when compared to flossing. It should be noted here however, that differences were substantial for both the gingivitis and plaque analyses most likely due to methodological and clinical variability between the studies. One included study concerns brushpicks which are not inter-dental brushes but a plastic toothpick with plastic filaments. These two systematic reviews on inter-dental brushes (Slot et al. 2008, Poklepovic et al. 2013) had five shared papers. The differences in their selection for each review was due to alternative inclusion criteria. It is recognized that different studies will provide different outcomes (Bowen 2012).

Schmage et al. (1999) assessed the relationship between the inter-dental space and the position of the teeth. Most of the inter-dental spaces in the anterior teeth are small with embrasure type 1, thus floss is more ideal. Premolars and molars have larger inter-dental spaces with embrasure type 2. They are more accessible with interdental brushes. Further, the primary advantage of inter-dental brushes is their superiority in reaching interdental groves or fissures. These cannot be physically cleaned by any other inter-dental cleaning device. This morphological component had not been used in any of the studies published so far. This makes matching in the random assignment and a true comparison among products difficult; hence, the grouping of all inter-dental brushes into one category (Gluch 2012).

Oral Irrigators

The oral irrigator is an oral hygiene aid that has been developed to assist plaque control and reduce gingival inflammation. Oral irrigators are designed to disturb soft debris and ideally remove biofilm via the mechanical action of a mildly pressurised stream of water. There has been considerable controversy regarding the appropriate use and efficacy of this method of interdental cleaning (van der Weijden & Slot 2011). Hussein et al. (2008) systematically reviewed the literature on the topic of the effect of an oral irrigator in combination with toothbrushing, on controlling plaque, gingival inflammation and pocket probing depth. They determined that there were insufficient studies to perform a meta-analysis. They did

note however, that the oral irrigator, as an adjunct to toothbrushing, does improve gingival health more than regular oral hygiene measures or toothbrushing alone.

There was no evidence suggesting any statically significant biofilm reduction. Further, a 4-week study indicated that oral irrigation in combination with manual toothbrushing was significantly more effective in reducing gingival bleeding scores than the use of dental floss as an interdental cleaning aid (Rosema et al. 2011). The precise mode of action that influences these observations is still unclear. It is thought that oral irrigation does not produce enough water pressure to disrupt and reduce mature biofilm, it may only interrupt newly formed biofilm, thereby interfering with maturation of the microbial biofilm, thereby, influencing gingival inflammation. Another possible effect is the mechanical action of a jet stream of the water and depending on the device, its pulsations, which may reduce the levels of inflammatory mediators in the gingival crevice/pocket, thereby contributing to improved gingival homeostasis and health (Chaves et al.1994, Flemmig et al. 1990, Frascella et al. 2000). Further, it is also possible that any benefit an oral irrigator may have in reducing inter-dental plaque, may be undetectable clinically.

As such, further studies are needed to research the effectiveness of the oral irrigator as an adjunct to regular oral hygiene measures for reducing interdental biofilm and for the long-term maintenance of gingival health (Jin 2009). To date systematic reviews did not specifically evaluate blunt-ended cannulae (WaterPiK Pik Pocket TM subgingival irrigation tip – Water Pik Inc., Fort Collins, CO, USA).

1.2. RATIONALE FOR PERFORMING THE STUDY

There are a number of studies, metanalysis or RCT's which identify further research is required into the efficacy of various interdental cleaning tools.

It is widely accepted teaching practice based upon evidence and recommendations of international associations e.g. the European society of Periodontology that for interdental embrasure types 2 and 3, interdental brushes are now the gold standard for efficient plaque removal and thus reduction in interdental gingival inflammation.

Patient compliance with interdental cleaning has always presented Oral Health clinicians with challenges. Patients have shown more interest in “cleaning devices” which could make the process more effortless.

If our study can determine if a properly calibrated oral irrigation, with standardized correct use of the device, compared to the correct sizing and use of Interdental brushes, can have a significant statistical benefit in plaque/gingival inflammation reduction, this may have a meaningful impact on future patient education.

2. HYPOTHESIS

Null hypothesis: there will be no significant difference in the efficacy of interdental brushes vs oral irrigation in the removal of plaque and the maintenance of periodontal health.

3. STUDY OBJECTIVES

3.1. PRIMARY OBJECTIVES

To undertake an ethical and independent study to determine whether there is any significant difference in the efficacy of interdental brushes vs Oral irrigation in the removal of plaque and the maintenance of periodontal health.

3.2. SECONDARY OBJECTIVES

To investigate the patient preference and ease of use for the interdental brushes and oral irrigation

4. STUDY DESIGN

4.1. DESIGN

Within-subjects experimental study design

4.2. EXPECTED PARTICIPANT NUMBERS

40 subjects would be enrolled into the study. A sample size calculation determined 34 participants were required for an effect size of 0.5, with $\alpha=0.05$ and $\beta=0.80$. An additional 20% is included to allow for dropouts.

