6.8. END OF STUDY TREATMENT/WITHDRAWAL PROCEDURE

A participant can leave the research study at any time. When withdrawing from the study, the participant should let the research team know that they wish to withdraw, either in person, by phone or by email. A participant may provide the research team with the reason(s) for leaving the study but is not required to provide their reason.

The final visit is complete with a final plaque removal, and instructions for routine regular care.

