8. STATISTICAL CONSIDERATIONS

8.1. SAMPLE SIZE OR POWER CALCULATION

40 subjects would be enrolled into the study. A sample size calculation determined 34 participants were required for an effect size of 0.4 (medium sample size approach), with $\alpha=0.05$ and $\beta=0.85$ (G*Power sample calculation software). An additional 20% is included to allow for dropouts.

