8.2. PROVIDE A DETAILED ANALYSIS PLAN

The analysis will be performed using PRISM (Version 8) statistical software, with the level of significance set at $p<0.05$. The difference in clinical parameters between baseline, and between interventions, will be evaluated using a “Paired t-test”.

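### Forty enrolled is slightly less than 34 plus 20%, keeps 34 complete pairs only if at most 6 are lost, and the paired t-test drops from the device comparison anyone who leaves after Visit 3

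*Protocol*

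**What the plan says.** Section 4.2 sets the target ("40 subjects would be enrolled into the study") and the requirement behind it: "A sample size calculation determined 34 participants were required for an effect size of 0.5", at 5% significance and with 0.80 given as beta, evidently meaning power. It then adds: "An additional 20% is included to allow for dropouts". Section 8.1 repeats the two counts ("40 subjects would be enrolled into the study. A sample size calculation determined 34 participants were required") and the 20% addition, but with effect size 0.4 and 0.85 in place of 0.5 and 0.80. The synopsis agrees with 8.1.

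Section 8.2 names one method. Differences from baseline and "between interventions, will be evaluated using a “Paired t-test". Under section 6.2 the outcome on the first device is measured at Visit 3 and on the second at Visit 5. Section 6.8 provides that "A participant can leave the research study at any time". The protocol describes no replacement of those who leave.

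**The concern.** Two things need checking.

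- **The allowance.** The step from 34 to 40 is described as 20%, and it is not quite that. An addition of 20% to the required number also protects against less than 20% loss from the enrolled number. Because 34 is the smallest number that reaches 0.80 under the section 4.2 inputs, there is no slack to absorb the difference.
- **The test.** The device comparison is the primary objective, and a paired test needs both a Visit 3 and a Visit 5 score. Someone who completes the first period and then leaves contributes nothing to it, although a valid score on one device exists. That wastes some information. It could also bias the comparison if people leave because of how they fared on the first device and do so more often with one device.

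**Working it through.** **Inputs.** Required 34; enrolled 40; addition 20% (4.2, 8.1, synopsis). Effect size 0.5 and power 0.80 (4.2), or 0.4 and 0.85 (8.1, synopsis). Alpha 0.05 (8.2). Two assumptions: the test is two-sided, because the objective asks about any difference, and the effect size is the mean paired difference divided by its SD, because the protocol does not name the type.

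**1. Reproducing the 34.** Power of a paired t-test comes from the noncentral t distribution with n − 1 degrees of freedom and noncentrality d√n.

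| Pairs | Power, d = 0.5 | Power, d = 0.4 |
|---|---|---|
| 32 | 0.782 | 0.592 |
| 33 | 0.795 | 0.606 |
| 34 | 0.808 | 0.620 |

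The section 4.2 inputs give exactly 34. The section 8.1 inputs do not: 0.4 with 0.85 needs 59 pairs two-sided, or 47 one-sided.

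**2. The uplift.** 34 × 1.20 = 40.8, so a full 20% addition needs 41. The actual uplift is 40/34 − 1 = 17.6%.

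**3. What 40 tolerates.** 40 − 34 = 6 losses, and 6/40 = 15%.

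**4. The two readings of 20%.**

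- As an addition to the required number, it corresponds to a loss of 1 − 1/1.20 = 16.7%. Then 40/1.20 = 33.3 pairs remain, just under 34.
- As a dropout rate, 40 × 0.80 = 32 pairs remain, 2 short. Power at d = 0.5 is 0.782, which is 0.808 − 0.782 = 0.026 lower than with 34 pairs and 0.018 below 0.80. Keeping 34 at that rate needs 34/0.80 = 42.5, that is 43 enrolled.

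**5. What the paired test gives up.** Assume 20 participants per sequence, 4 in each lost after Visit 3, outcome variance 1 and within-person correlation r. The variance of the device effect is as follows.

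- Complete pairs only (16 per sequence): 2(1 − r)/(4 × 16) × 2. At r = 0.5 this is 0.03125.
- All available scores, with device and period fixed and participant random: 2(v11·v22 − v12²)/(v11 + v22 + 2·v12), where v11 = 1/20, v12 = r/20 and v22 = (1 − r²)/16 + r²/20. At r = 0.5, v11 = 0.05, v12 = 0.025 and v22 = 0.046875 + 0.0125 = 0.059375. The result is 2 × 0.00234375/0.159375 = 0.02941.

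The ratio is 0.02941/0.03125 = 0.94. At r = 0.3 and 0.7 it is 0.92 and 0.96. Keeping the Visit 3 scores therefore cuts the variance by 4 to 8%. This is the most it can do for 8 evenly split losses, because nothing is recovered from anyone lost before Visit 3.

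**6. Bias, under assumed scenarios only.** A simulation took no true difference, 8 of 40 lost after Visit 3, those lost being the worst Visit 3 scorers, and r from 0.3 to 0.7.

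| Losses by sequence | Bias of paired difference | Type I error |
|---|---|---|
| 4 and 4 | none | not inflated by bias |
| 6 and 2 | 0.2 to 0.4 SE | 5 to 7% |
| 8 and 0 | 0.5 to 0.8 SE | 8 to 13% |

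The model that keeps the Visit 3 scores showed no bias in these scenarios.

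**The case against.** The strongest reply is that the protocol describes an amount added to 34 and states no expected dropout rate. On those words 40 is 40.8 rounded down, less than one person short. That is correct, and it rules out a tempting stronger reading: that the protocol plans for 20% dropout and misses its own requirement at that rate. The figure of 32 pairs follows only if the 20% is reinterpreted as a loss rate. What stands is that 40 falls short on both readings, by 1 participant (41) or by 3 (43), and that its true tolerance of 15% is nowhere stated.

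A second reply is that handling of missing data may be left to an analysis plan that is not at hand. That is fair for analysis sets and missing-data rules, and their absence is not the point here. But section 8.2 does fix the test for the device comparison, and that test works only on complete pairs.

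A third is that the test does not lose these participants altogether. That is right: someone who leaves after Visit 3 still supplies a Visit 2 to Visit 3 pair for the planned comparison with baseline. Only the device comparison loses them.

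Finally, the bias scenarios are constructed. Participants know which device they are using, so device-related withdrawal is possible. But nothing in the protocol indicates that it will occur, that the worst scorers will leave, or that losses will be uneven. Some losses may also come before any outcome is measured, since enrolment precedes the first assessment by two weeks.

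**Conclusion.** The point holds in a limited form. The 20% allowance is slightly misstated: 40 is a 17.6% uplift and protects 34 pairs against at most 6 losses (15%). If 20% is meant as a dropout rate, 32 pairs remain and power is 0.78 instead of 0.80. This assumes a two-sided paired test and the section 4.2 effect size of 0.5. It is a small shortfall and does not by itself undermine the trial.

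The paired t-test is also a less efficient choice than one that keeps Visit 3 scores, by at most about 4 to 8% of variance if all 8 losses fall after Visit 3. A reader might infer that the planned comparison is biased. The documents do not support that: bias needs outcome-related losses that differ between sequences, and this is an assumption.

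The conflict between 0.5 with 0.80 and 0.4 with 0.85 is a larger and separate matter. It bears on this one because the allowance rests on whichever requirement survives.

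**What to change.** 1. **Reconcile the inputs first.** Choose one effect size and power for section 4.2, section 8.1 and the synopsis. Then restate the dropout allowance in the same words in all three. If 34 with 0.5 and 0.80 is kept, say either that 40 enrolled tolerates 6 losses (15%), or that 20% dropout leaves 32 pairs with power 0.78. Neither statement should go into section 8.1 or the synopsis while these still carry 0.4 and 0.85, because it would contradict them: at 0.4, power is 0.62 with 34 pairs and 0.59 with 32.
2. **Change the device comparison in section 8.2.** Use a linear mixed model with device and period as fixed effects and participant as a random effect, fitted to every available Visit 3 and Visit 5 score. Report the complete-pair t-test as a sensitivity analysis.

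The cost is wording in three places and one additional model, with no extra participants or visits. The downsides are a slightly less favourable stated figure and reliance on data being missing at random. The gain in precision is modest.

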4.3. DURATION OF THE STUDY

The study will take approximately 18 months.

May 2021 – Ethics application

June 2021 – December 2021 - Recruitment/Data Collection

January 2022- Data analysis

JFeb-April 2022- Writing up

4.4. PRIMARY ENDPOINT data collection - 9 weeks after initial visit (Visit 1)

4.5. CENTRES

Sydney Dental Hospital - Level 4

5. STUDY PARTICIPANTS

5.1. INCLUSION CRITERIA

1. Disease status/ or disease group for study: Embrasure space of 2 or 3. PSR code \leq 3.
2. Gender: no restrictions
3. Age range: >18 years
4. At least 24 natural teeth
5. Willingness to provide informed consent and willingness to participate and comply with the study requirements.
6. Women of childbearing potential who are using a reliable contraceptive method(s).
7. Patients from all dietary backgrounds

[figure not shown]
5.2. EXCLUSION CRITERIA

1. Women lactating, pregnant or of childbearing potential who are not willing to avoid becoming pregnant during the study.
2. Participants with a history of active periodontal disease with a PSR code of 4.
3. Participants with a history of diabetes, tobacco smoking, xerostomia (dry mouth), any form of chronic inflammatory disease.
4. Participants who have taken antibiotics within the past six weeks.

5. Participants currently experiencing psychological illness or other conditions which may interfere with their ability to understand the study requirements or interfere with their motivation to participate in the study, or the evaluation of the study outcome.
6. As the following medication(s) can have interactive effects and may interfere with the participant's ability to meet the study requirements, they cannot be administered during the clinical study (anticoagulants, anti-convulsant, immunosuppressants, tricyclic antidepressants)
7. Participants that have a medical condition which inhibits their ability to safely use the OH tools, e.g. multiple sclerosis, Parkinson's disease.

6. STUDY PROCEDURES

6.1. STUDY FLOW CHART

6.2. INVESTIGATION PLAN

Methodology

Patients attending the clinics at the Sydney Dental Hospital will be invited to participate. BOH, DDS, or Postgraduate Periodontics students providing examinations to patients would assess them for eligibility; provided they met the inclusion and exclusion criteria the patients would then be provided with a Plain Language Statement and Consent form to consider participation. The participants will be given 2 weeks to consider their wish to participate or not and will be asked to call to book in for an appointment to participate in the study should they not wish to consent in writing on the day. A signed consent form will be required prior the participant being admitted into the study.

Visit 1. Is the enrolment visit, study participants would complete their consent form, and will receive a study enrolment number and this will be documented in the participant's medical (or personal) record and on all study documents. Further, they will receive an initial full mouth debridement involving plaque/stain

and gross supra gingival calculus removal using Hand instruments, Ultrasonic instruments and AirFlow (EMS AirFlow) with (PLUS Erythritol powder). There is a 2-week break between Visit 1 and Visit 2.

At **Visit 2**, the following clinical parameters will be assessed:

- Periodontal screening and recording (PSR)
- Modified papilla bleeding index
- Rustogi modified navy plaque index – teeth would be disclosed, and intraoral photos will be taken and assessed later.

Clinical parameters would be assessed by clinical examination by two calibrated, blinded examiners (registered dental practitioners).

Participants will again receive plaque/stain and residual supra gingival calculus removal using Hand instruments, Ultrasonic instruments and AirFlow (EMS AirFlow) with (PLUS Erythritol powder). Project assistants would provide a randomized allocation (using randomized envelopes) to either the interdental brush or water flosser and provide calibrated oral hygiene instructions appropriate to the allocation. Participants would use their allocated interproximal aid for 4 weeks.

Visit 3, clinical parameters will be assessed. Photographs of their teeth and gums taken to accurately record Modified papilla bleeding index and the Rustogi modified navy plaque index. There will be a “washout” period of 2 weeks when the participants will be asked to return to their normal routine for interdental cleaning, they undertook prior to the study commencing.

Visit 4, the Participants would have all plaque removed only with EMS AirFlow. Again, project assistants would provide calibrated oral hygiene instructions appropriate to the 2nd allocation. Participants would use their allocated interproximal aid for 4 weeks.

Visit 5, clinical parameters will be assessed. Photographs of their teeth and gums taken to accurately record Modified papilla bleeding index and the Rustogi modified navy plaque index, Finally, participants will be asked to complete a anonymous satisfaction survey.

Interventions	Visit 1	Visit 2	Visit 3	Visit 4	Visit 5
Participant Consent	✓				
Inclusion / Exclusion criteria	✓				
Initial full mouth debridement	✓				
Data collection/examination		✓	✓		✓
Plaque removal (airflow)		✓		✓	✓
Blinded allocation		✓			
OHI		✓		✓	
Patient survey					✓
Adverse Event & Serious Adverse Event Assessment					✓

Note: All study procedures are performed as part of routine dental practice.

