7. OUTCOMES

7.1. DEFINITION OF OUTCOMES

Periodontal screening and recording (PSR)

Divide the mouth into sextants. Using a periodontal probe, check six sites on each tooth, but the worst finding in the sextant determines the code.

Code definitions (Landry & Jean, 2002)

Code 0 Absence of clinical signs

Code 1 Bleeding on probing

Code 2 Supra and/or subgingival calculus and/or defective margins

Code 3 Periodontal pocket 4mm to 5.5 mm deep

Code 4 Periodontal pocket 6mm deep

Modified papilla bleeding index

Barnett et al. (1980) modified the PBI index (Muhlemann, 1977) by stipulating that the periodontal probe should be gently placed in the gingival sulcus at the mesial line angle of the tooth surface to be examined and carefully swept forward into the mesial papilla. They timed the appearance of bleeding and graded it as follows:

0 = no bleeding within 30 s of probing;

1 = bleeding between 3 and 30 s of probing;

[figure not shown]
2 = bleeding within 2 s of probing;

3 = bleeding immediately upon probe placement.

The mesial papillae of all teeth present from the second molar to the lateral incisor were assessed. Indices were derived for the maxillary left and mandibular right buccal segments, and the maxillary right and mandibular left lingual segments, and from these a full-mouth index was calculated. This distribution of test sites was utilized since each mesial papilla could only be tested once, i.e. from either the buccal or lingual side. They showed that the modified PBI may be more sensitive than the visual aspects of the GI in assessing changes in gingival health

Rustogi modified navy plaque index

To assess plaque present on teeth, the Modified Navy Plaque Index, developed by Rustogi et al., will be used. Disclosed plaque is scored in each tooth area as present (scored as 1) or absent (scored as 0) and recorded for both buccal and lingual surfaces. Tooth area plaque scores are grouped and designated as Whole mouth = Areas A, B, C, D, E, F, G, H and I, Marginal (gumline) = Areas A, B and C only, Approximal = Areas D and F only.

Patient satisfaction

A short survey to determine participant preference and ease of use for the interdental brushes (Brand: Curaprox) and oral irrigation device (Brand: “Waterpik” Pic Pocket™ subgingival irrigation tip) has been designed by the researchers. It consists of nine short questions.

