9.3. CASE REPORT FORMS AND SCHEDULE FOR COMPLETION

Participant demographics, clinical outcomes data, and survey responses are entered an excel spreadsheet. Some data will be interpreted by study investigators, and these interpretations will be coded and also entered into the spreadsheet. The data will then be reviewed to be sure that entries make sense and are internally consistent.

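### The only survey and the only scheduled adverse event enquiry come six weeks after the first device but directly after the second, and a truly anonymous survey may leave an order effect uncheckable

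*Protocol*

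**What the plan says.** The only secondary objective (Protocol Section 3.2) is "To investigate the patient preference and ease of use for the interdental brushes and oral irrigation". It rests on one researcher-designed survey, of which Section 7.1 says: "It consists of nine short questions". The questionnaire itself is an appendix and is not shown.

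Section 6.2 places the survey at Visit 5, where "participants will be asked to complete a anonymous satisfaction survey". In the visit table of the same section, the patient survey row and the row "Adverse Event & Serious Adverse Event Assessment" each carry one tick, under Visit 5.

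Other sections bear on the point:

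- Sections 6.2 and 6.5 give each participant an enrolment number that is to appear on every study document.
- Section 9.3 states: "Participant demographics, clinical outcomes data, and survey responses are entered an excel spreadsheet".
- Section 12.1 asks participants with gingival trauma to book an early appointment with the researchers. Section 6.3 says incidents will be reviewed and treated.
- Section 12.2 has serious adverse events reported at once, with follow-up reports under a participant code.
- Section 13 keeps the allocations in a separate spreadsheet.

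**The concern.** Each participant uses both devices in random order, and the secondary objective compares them. If both are rated on one occasion, straight after the second, the two ratings do not rest on the same quality of memory. The first is recalled across a washout and a full period on the other device; the second is fresh. Minor adverse events have the same problem: small trauma from the first device that was not reported when it happened may be forgotten, or placed in the wrong period, by the time anyone asks.

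Anonymity adds a second difficulty. If an answer cannot be joined to the participant's sequence, no later analysis can examine whether the device used last was favoured because it was last. This is fixed when the data are collected, so a statistical analysis plan cannot repair it.

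**Working it through.** **Timing.** The protocol gives no recall interval, so there is no figure to reproduce. It follows from the intervals in Section 6.2:

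- Visit 1 to Visit 2: "There is a 2-week break between Visit 1 and Visit 2".
- Visit 2 to Visit 3, first device: "Participants would use their allocated interproximal aid for 4 weeks".
- Visit 3 to Visit 4, washout: a "period of 2 weeks when the participants will be asked to return to their normal routine for interdental cleaning".
- Visit 4 to Visit 5, second device: again 4 weeks.

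With Visit 1 at week 0:

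- Visit 2 = 0 + 2 = week 2
- Visit 3 = 2 + 4 = week 6
- Visit 4 = 6 + 2 = week 8
- Visit 5 = 8 + 4 = week 12

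Lag from use to the survey and the scheduled adverse event enquiry:

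- end of first device: 12 − 6 = 6 weeks
- start of first device: 12 − 2 = 10 weeks
- end of second device: 12 − 12 = 0 weeks

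An unreported event on the first device is thus first asked about 6 to 10 weeks after it occurred. With an enquiry at Visit 3, the lag from the end of first-device use would be 6 − 6 = 0 weeks, the same as for the second device. Section 4.4 puts primary endpoint collection at 9 weeks after Visit 1, which matches none of these visits; the lags above use the visit schedule.

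**Early leavers.** Sections 6.8 and 6.9 let participants leave at any time without giving a reason. The plan enrols 40 and requires 34 (Sections 4.2 and 8.1), a margin of 40 − 34 = 6, or 6/40 = 15%. If that many left before Visit 5, 6 participants would give no survey answer and receive no scheduled adverse event enquiry, including any who had completed the first period.

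**Effect of recency on preference.** Take a simple model, assumed here for illustration. Let p be the true share preferring device A, q the share who simply name the device used last, and s the share who used A second. The observed share is (1 − q)p + qs.

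- With balanced sequences, s = 1/2, and the departure from 1/2 becomes (1 − q)(p − 1/2). A true preference is shrunk, not reversed.
- With unbalanced sequences, a further term q(s − 1/2) is added, in favour of whichever device more often came second.

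The protocol gives no values for p, q or s. Section 6.7 describes randomised envelopes without stating that the two orders are balanced. Estimating q requires answers split by sequence, which an unlinked survey does not provide.

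**Can records be linked?**

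- *Survey.* The description as anonymous in Section 6.2 points one way. The enrolment number on every study document (Sections 6.2 and 6.5) points the other, and Section 9.3 has survey answers entered in a spreadsheet along with demographics and clinical outcomes. These statements do not fit together.
- *Adverse events.* Nothing calls these records anonymous. The enrolment number and the allocation spreadsheet allow each to be joined to sequence.

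**The case against.** A reader might infer that adverse events are captured only at Visit 5. The protocol does not support that. Sections 12.1 and 12.2 provide for self-report and for immediate reporting of serious events at any time. At Visit 3 the gingiva is also examined, probed for bleeding and photographed, so the end of first-device use is not unobserved. What remains is that no scheduled question about adverse events is put to the participant at that visit.

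A reader might also infer that neither preference nor adverse events can be tied to device order. For adverse events this is wrong, as shown above. For the survey it is unproven: the questionnaire may ask which device came first, and anonymous may be loose wording for coded.

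Nor is the timing of the preference question at fault. A comparative preference can only be asked after both devices have been used, so Visit 5 is the right visit. The recall gap concerns first-device ease of use and satisfaction.

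Finally, order is randomised, so recency does not systematically favour one product when the sequences are about equal in size. That stands: the main costs are dilution and an order effect that cannot be examined. Anonymity also has a purpose, since people may answer more freely. The choice of test for the survey can be left to the statistical analysis plan.

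None of this removes the unequal recall, the missing enquiry for early leavers, or the conflict over whether the survey is identifiable.

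**Conclusion.** The point holds in a limited form, as a cheap improvement of minor severity. Followed as written, the visit table gives a 6-week recall gap for the first device and none for the second, in every participant who reaches Visit 5, for ease of use and for non-serious events not self-reported. Participants who leave earlier are not asked at all. This rests on the intervals in Section 6.2 and on the table ticks as shown.

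The statement that an order effect cannot be checked is conditional on two things: the survey being truly anonymous, and the unseen questionnaire not asking device order. The conflict between the anonymous survey and the enrolment number on every study document needs reconciling either way.

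The size of any distortion in preference or in adverse event counts cannot be derived from the protocol. The primary comparison of plaque and periodontal measures is not affected.

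**What to change.** - Reconcile the description of the survey in Section 6.2 with the enrolment-number rule in Sections 6.2 and 6.5 by making the survey coded, carrying the enrolment number and no name.
- Ask the ease-of-use items about the device just used at Visit 3, and again at Visit 5. Keep the comparative preference item at Visit 5.
- In the visit table, tick adverse event assessment at Visit 3 as well as Visit 5, and record the device in use at onset.
- Have the project assistant, who already handles allocation, make the enquiry, so that the examiners stay blinded as Section 13 requires.

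The cost is a few minutes at an existing visit, with no new visit, and a wording change to the survey and, where it promises anonymity, to the participant information. Under Section 10.3 the amendment needs ethics approval before use. The one drawback is that coded answers may be slightly less candid.
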